Medical charts will be abstracted for imaging and pathologic findings. Patients will undergo their one additional MR sequence as part of their clinical MRI brain scan. This additional sequence will be included prior to IV contrast administration as part of the standard MR brain without and with IV contrast examination.

Commercially available MRI scanners (General Electric (GE) Medical Systems, Wauwatosa, WI, USA at both 1.5T and 3T and Siemens, Siemens Healthcare, Germany) will be used.

Study Procedure

Commercially available MRI scanners (General Electric (GE) Medical Systems, Wauwatosa, WI, USA at both 1.5T and 3T and Siemens, Siemens Healthcare, Germany at both 1.5T and 3T) will be used. A total of 40 patients will be recruited and randomly selected from the cohort of patients undergoing a MR brain without and with IV contrast examination on the Siemens 1.5T and 3T, and GE 1.5T and 3T MR scanners within the clinic. The additional sequence will be a sagittal T1 CUBE FS for the GE scanners and a sagittal T1 SPACE FS for the Siemens scanners.

The additional sequence will be anonymized and stored for subsequent analysis using the machine learning model as part of the training phase.

This study involves the development of an AI algorithm which analyze images from routine Brain without and with IV contrast agent (Gadolinium (Gd)) examinations to confirm that Gd contrast agent has been correctly administered. The training and testing data will include both prospective and retrospective MR data. We require additional data which simulates the occurrence of IV infiltration during a routine brain without and with IV contrast exam as currently there is a low number of previous studies (n= 50) with associated MR images demonstrating IV infiltration. The data collected as part of this innovation study will be used to augment the retrospective data already collected for the training and testing of the developed AI algorithm.

The machine learning training and testing process is described below and illustrated in Figure 1.

- i. Training Phase - Predictive machine learning models for detection of infiltration will be developed and the performance optimized. Machine Learning Tasks will be to (a) differentiate nasal mucosa with Gd contrast agent uptake vs. nasal mucosa or eye fat ratio without Gd contrast agent uptake.

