- ii. Test Phase - Evaluate the machine learning model and then compare them with the assessment by radiologists using McNemar's test and Receiver Operator Curve (ROC) analysis with specificity threshold equivalent to clinical reporting.

[figure not shown]

Figure 1: (a) Radiomics Machine Learning model development and training workflow. (b) (i) During training, the network weights will be optimized according to the error calculated by the binary loss function; (ii) After each training epoch, the model performance will be assessed by the area under the receiver-operating characteristic curve (AUC) on the validation set; (iii) The parameters of the model predictions will be recalibrated using the unseen calibration dataset and (iv) Model testing will be carried out in the unseen test cohort using the best performing model identified from the validation set and the performance will be evaluated using receiver-operator characteristic curve analysis, net benefit analysis and intra-class correlation coefficient.

Subject Information

Target accrual is the proposed total number of subjects to be included in this study at Mayo Clinic. A "Subject" may include medical records, images, or specimens generated at Mayo Clinic and/or received from external sources.

Target accrual: 40

Subject population (children, adults, groups): Adults undergoing MR brain without and with IV contrast examination as part of their care plan.

Inclusion Criteria:

Patients undergoing a MR brain without and with contrast examination on any GE or Siemens 1.5T and 3T MRI system within Mayo Clinic, Rochester, as part of their care plan.

Exclusion Criteria:

Pregnant Women and individuals under the age of 18 years.

Review of medical records, images, specimens

Check all that apply (data includes medical records, images, specimens).

Only data that exists before the IRB submission date will be collected.

Date Range for Specimens and/or Review of Medical Records:

Note: The Date Range must include the period for collection of baseline data, as well as follow-up data, if applicable.

The study involves data that exist at the time of IRB submission **and** data that will be generated after IRB submission. Include this activity in the Methods section.

Examples

- The study plans to recruit subjects undergoing a MR brain without and with IV contrast examination as part of their care plan.

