The study will use data that have been collected under another IRB protocol. Include in the Methods section and enter the IRB number from which the research material will be obtained. *When appropriate, note when subjects have provided consent for future use of their data and/or specimens as described in this protocol.*

Enter one IRB number per line, add more lines as needed

Data Specimens Data & Specimens _____

Data Specimens Data & Specimens _____

Data Specimens Data & Specimens _____

Data Analysis

Power analyses may not be appropriate if this is a feasibility or pilot study, but end-point analysis plans are always appropriate even if only exploratory. Provide all information requested below, or provide justification if not including all of the information.

Power Statement: Not applicable – pilot study

Data Analysis Plan:

Receiver operating characteristic (ROC) curves will be generated for radiologist diagnosis and the machine learning models decisions and compared using the Delong test. Cut-off values for the machine learning models will be selected to match the sensitivity of radiologist clinical assessment in the training cohort, in order to construct working points of the models that maintain clinically achieved detection rates for the specific clinical exams. The sensitivity and specificity of the machine learning models will be compared based on the reduction of false-positive (FP) decisions compared with the clinical reference. The performance of the machine learning models will be compared to that of the radiologist performance using the McNemar test.

Endpoints

Primary: Area-under-curve performance for each machine learning model and the performance measure “net benefit”. Net benefit is defined as:

$$\text{Net benefit} = \frac{\text{True positives}}{\text{Total number of patients}} - \frac{\text{False positives}}{\text{Total number of patients}} \times w$$

The weighting factor, w , corresponds to the odds (i.e. the harm-to-benefit ratio) of the chosen risk threshold. Retest-repeatability of the model determined from intra-class correlation coefficient (ICC).

Secondary: Sensitivity and specificity of each machine learning model and comparison with radiologist performance using the McNemar test.

References

1. OECD Health Statistics. Health care utilisation. OECD. Stat Web site. Available at: http://stats.oecd.org/Index.aspx?DataSetCode=HEALTH_PROC.

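### The protocol sets the model's operating point by two conflicting rules, and ties the sensitivity rule to the cohort on which the model is trained

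*Protocol*

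**What the plan says.** Two places in the protocol describe where on the ROC curve the model is compared with the radiologists.

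- **Study Procedure, item ii (Test Phase):** the comparison uses McNemar's test and "Receiver Operator Curve (ROC) analysis with specificity threshold equivalent to clinical reporting".
- **Data Analysis Plan:** "Cut-off values for the machine learning models will be selected to match the sensitivity of radiologist clinical assessment in the training cohort". The purpose given is "in order to construct working points of the models that maintain clinically achieved detection rates for the specific clinical exams". Models are then "compared based on the reduction of false-positive (FP) decisions compared with the clinical reference", and McNemar's test is named again.

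The results that use the cut-off include the secondary endpoint: "Sensitivity and specificity of each machine learning model and comparison with radiologist performance using the McNemar test".

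The Figure 1 legend describes separate validation, calibration and unseen test sets. On fitting it says: "During training, the network weights will be optimized according to the error calculated by the binary loss function". It does not link the cut-off to any of the held-out sets, and it does not say whether the cut-off is set before or after recalibration.

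**The concern.** A single cut-off can match the radiologists on sensitivity or on specificity, but in general not on both. With neither rule said to govern, one fitted model can yield two sets of secondary results, and the choice could be made after seeing them. The specificity rule also defeats the plan's own comparison: if the model's specificity is set equal to the radiologists', its false-positive rate equals theirs in expectation and there is no reduction to find.

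The training cohort raises a second problem. On its plain reading, the Data Analysis Plan sets the cut-off on cases whose labels were used to fit the weights. Scores for those cases tend to be too well separated, so a cut-off that keeps the target share of training positives keeps fewer new ones. That works against the stated aim of preserving the detection rate achieved in the clinic.

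**Working it through.** The protocol gives no reader accuracy, feature count or split sizes, so it has no figure of its own to reproduce. It does give 50 retrospective infiltrated studies ("currently there is a low number of previous studies (n= 50) with associated MR images demonstrating IV infiltration") and 40 prospective patients whose extra pre-contrast sequence simulates infiltration. All other inputs below are assumptions.

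**1. Two rules, two operating points.** Assume an equal-variance binormal ROC curve and radiologists at 90% sensitivity and 95% specificity.

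- d′ = √2 · Φ⁻¹(AUC)
- Sensitivity matched: specificity = Φ(d′ − 1.282)
- Specificity matched: sensitivity = Φ(d′ − 1.645)
- False positives per 100 negatives = 100 × (1 − specificity); the radiologists have 5.0

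| Model AUC | d′ | Sensitivity rule (sens/spec) | Specificity rule (sens/spec) | False positives per 100 negatives, sensitivity v specificity rule |
|---|---|---|---|---|
| 0.95 | 2.326 | 90.0% / 85.2% | 75.2% / 95.0% | 14.8 v 5.0 |
| 0.98 | 2.904 | 90.0% / 94.8% | 89.6% / 95.0% | 5.2 v 5.0 |
| 0.99 | 3.290 | 90.0% / 97.8% | 95.0% / 95.0% | 2.2 v 5.0 |

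The assumed radiologist point corresponds to a binormal AUC of 0.981, which is why the rules nearly agree at 0.98. Away from it they diverge. Under the specificity rule the false-positive count stays at 5.0 whatever the model's quality.

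With radiologists at 80%/95% the pattern is the same. AUC 0.90 gives 80%/83.4% v 56.7%/95%, and AUC 0.98 gives 80%/98.0% v 89.6%/95%.

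**2. Cut-off set on training scores.** The simulation used 1,000 runs per setting, balanced classes and a linear discriminant with shrinkage 0.1. The population d′ was 2.326, spread over up to 5 features. The cut-off kept at least 90% of training positives and was then applied to new cases. The two sizes are 50 positives and 50 + 40 = 90. Both assume that every positive is used for development, so real splits would be smaller.

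| Features | Mean test sensitivity, 50 positives | Mean test sensitivity, 90 positives |
|---|---|---|
| 1 | 88.3% | 88.9% |
| 5 | 86.8% | 88.2% |
| 10 | 84.6% | 86.9% |
| 20 | 80.3% | 85.1% |
| 40 | 70.7% | 79.8% |

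Part of the gap from 90% is not due to training scores. Keeping 45 of 50 positives has expected sensitivity 45/51 = 88.2% even on unseen scores, and keeping 81 of 90 has 81/91 = 89.0%. A 10-fold out-of-fold cut-off on the same data gave about 88% to 90% at every feature count. The loss attributable to training scores is therefore about 0 to 2 points with 1 to 5 features, 2 to 4 with 10, and 4 to 19 with 20 to 40.

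**3. Sensitivity to the classifier.** An unshrunk discriminant at attainable AUC 0.90 gave 88%, 87%, 84%, 79% and 67% with 50 positives, for 1, 5, 10, 20 and 40 features. A cut-off set on as many held-out positives gave 88% to 89%. With heavy shrinkage (0.9), the loss at 40 features falls to about 8 or 9 points with 50 positives and about 4 with 90. The direction holds for multi-feature models; the size does not carry over from one model to another.

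**The case against.** The Test Phase sentence never uses the word cut-off, and its specificity clause may qualify only the ROC analysis, as a second reading of the curve beside the sensitivity-matched point. The Data Analysis Plan holds the only explicit cut-off rule and is coherent alone. That reading is possible, but the protocol does not state it, and the clause stands in the same sentence as McNemar's test. If it is what was meant, the clause needs a label.

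The reference to the training cohort may say only where radiologist sensitivity is measured, or may mean development data in general. Fixing the cut-off outside the test cohort is sound practice, and the plan deserves credit for that. Still, no other data set is named for the model's cut-off, and the conflict between the two rules stands on any reading.

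Every numerical input is assumed, and the simulation leaves out model selection on validation AUC and recalibration. The task, built on nasal mucosa uptake or an eye fat ratio, need not produce a high-dimensional model; with one feature there is no training-score loss. This limits the size of the second point and leaves its direction for multi-feature models intact.

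The study is a pilot and only secondary results are touched. That bears on severity. It excuses a missing power statement, but not two incompatible rules for one comparison.

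**Conclusion.** The concern holds and should be fixed. The conflict between the rules is in the text and needs no assumed inputs. Its effect ranges from negligible, when the model's ROC curve passes near the radiologists' point, to about 15 points of sensitivity (90.0 − 75.2 = 14.8) and 10 of specificity (95.0 − 85.2 = 9.8) in the AUC 0.95 example. The loss from a training-cohort cut-off is general in direction for multi-feature models. Its size depends on model flexibility and regularisation, which the protocol does not give. The primary AUC does not use the cut-off, and net benefit has its own risk threshold.

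**What to change.** Make matching on radiologist sensitivity the governing rule in both places, because the planned false-positive comparison requires it. In the Test Phase text, delete the specificity clause or label it a secondary analysis. Suggested wording for the Data Analysis Plan:

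> The cut-off is the value at which out-of-fold (cross-validated) sensitivity in the development data equals radiologist sensitivity on cases with a clinical read. It is fixed before the test cohort is opened, on the score scale applied there.

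Report test sensitivity with a confidence interval beside the false-positive comparison, so that any shortfall in detection is visible.

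Use the unseen calibration set for the cut-off only if it holds enough positives. Keeping r of m positives gives a sensitivity distributed as Beta(r, m + 1 − r). With 9 of 10 the mean is 9/11 = 81.8% (SD 11.1 points, below 90% in 74% of draws). With 18 of 20 it is 18/21 = 85.7% (SD 7.5 points).

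The cost is wording in two places and cross-validated refits, with no new patients. The refits add a step to the Figure 1 workflow, and their scores must be brought to the scale of the final recalibrated model. The cut-off stays noisy: the out-of-fold version has an SD of about 5 points with 50 positives and 3.5 with 90, and roughly half to 64% of runs still fall below 90%. It removes the training-score loss but not the sampling error.

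### The cut-off is matched to radiologist sensitivity in a training cohort that can hold up to 40 simulated infiltrations without a clinical radiologist assessment, so the working point can miss its stated aim

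*Protocol*

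**What the plan says.** The protocol (Data Analysis, Data Analysis Plan) fixes the rule for the working point: "Cut-off values for the machine learning models will be selected to match the sensitivity of radiologist clinical assessment in the training cohort". The sentence goes on to give the purpose: "in order to construct working points of the models that maintain clinically achieved detection rates for the specific clinical exams".

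What the training cohort contains is set out elsewhere:

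- Subject Information gives "Target accrual: 40". Under Methods, each patient has one extra sequence: "This additional sequence will be included prior to IV contrast administration".
- Study Procedure explains why it is needed: "We require additional data which simulates the occurrence of IV infiltration during a routine brain without and with IV contrast exam". The reason given is that "currently there is a low number of previous studies (n= 50) with associated MR images demonstrating IV infiltration".
- Study Procedure then says where the series go: "The additional sequence will be anonymized and stored for subsequent analysis using the machine learning model as part of the training phase". The same section also says that the prospective data will be "used to augment the retrospective data already collected for the training and testing of the developed AI algorithm", which is wider than training alone.

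On the operating point there is a second statement. The Test Phase item in Study Procedure names a threshold on specificity, set to correspond to clinical reporting, whereas the Data Analysis Plan matches on sensitivity.

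**The concern.** Matching a model to a reader on sensitivity makes sense only if both are scored on the same positive cases. Here the cohort named for the matching can include series acquired before any gadolinium was given. These serve as positives for the model, but no clinical assessment of infiltration can have been made on them. The radiologist's clinical sensitivity can come only from genuine infiltrations, while the model's sensitivity in the same named cohort may also count the simulated ones.

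If the simulated series are easier for the model, part of the sensitivity target is met through them, and the cut-off can be stricter than one matched on genuine cases alone. A stricter cut-off misses more genuine infiltrations and cannot increase false positives. The planned comparison on reduction of false positives would then look better partly because genuine infiltrations are missed. Timely detection of infiltration is the study's stated reason, so the missed cases are the costly ones.

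**Working it through.** The protocol gives no radiologist sensitivity, model sensitivity or power figure, so there is no stated result to reproduce. The question is how far pooled matching can move sensitivity for genuine cases.

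**Inputs from the protocol**
- Simulated positives: m = 40 at most (Subject Information; Study Procedure).
- Genuine infiltration studies: 50 in total (Study Procedure). The split between training and the other datasets is not given, so g, the number in training, is at most 50.

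**Assumptions**
- Radiologist sensitivity S: 0.80, 0.90 or 0.95.
- Model sensitivity on simulated positives, Se_sim: 1.00 or 0.95.
- Genuine training positives g: 50, 30 or 25.
- Pooled matching: the model's sensitivity is computed over genuine and simulated positives together.

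**Formula**

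Pooled model sensitivity = (g × Se_gen + m × Se_sim) / (g + m). Setting this equal to S gives

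Se_gen = (S × (g + m) − m × Se_sim) / g = S − (Se_sim − S) × m/g.

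The shortfall is therefore (Se_sim − S) × m/g. It is positive only if the model detects simulated cases more often than S, zero if equally often, and negative otherwise.

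**Main case, g = 50, S = 0.90**
- All simulated cases detected: (0.90 × 90 − 40)/50 = 41/50 = 0.82.
- 95% detected: (0.90 × 90 − 38)/50 = 43/50 = 0.86.

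**Range of Se_gen, m = 40**

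| g | Simulated share of positives | Se_sim | S = 0.80 | S = 0.90 | S = 0.95 |
|---|---|---|---|---|---|
| 50 | 40/90 = 44% | 1.00 | 0.64 | 0.82 | 0.91 |
| 50 | 44% | 0.95 | 0.68 | 0.86 | 0.95 |
| 30 | 40/70 = 57% | 1.00 | 0.53 | 0.77 | 0.88 |
| 30 | 57% | 0.95 | 0.60 | 0.83 | 0.95 |
| 25 | 40/65 = 62% | 1.00 | 0.48 | 0.74 | 0.87 |
| 25 | 62% | 0.95 | 0.56 | 0.82 | 0.95 |

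The rows for g = 30 and 25 keep all 40 simulated series in training while some genuine cases go elsewhere, which is the unfavourable combination. If both sources are split in the same proportion, m/g stays at 40/50 and the g = 50 rows apply.

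**Check on direction.** A unit-variance binormal score model at S = 0.90, g = 50, m = 40, with the pooled cut-off solved numerically, gives:
- simulated easier (separation from negatives 3 v 2 for genuine): Se_gen = 0.84
- equal difficulty: Se_gen = 0.90, no shortfall
- simulated harder (2 v 3): Se_gen = 0.97, above the radiologist

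**After the change.** If matching uses only genuine exams, Se_gen equals S in the training cohort by construction, up to the steps that a finite sample allows. The price is precision: 45/50 has an exact 95% confidence interval of 0.78 to 0.97, and 27/30 one of 0.73 to 0.98.

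**The case against.** The strongest reply is that the rule already means what it should. It speaks of a clinical assessment by radiologists and of the specific clinical exams, so a sensible analyst would match only on exams that have such an assessment. Nothing says that simulated positives are pooled into the model's sensitivity. This benign reading is available. But the text names the training cohort as the matching set and, in another section, puts the simulated series into the training phase, without stating an exclusion. A separate SAP could settle it; as it stands, the protocol names the cohort and leaves the conflict open.

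Three stronger conclusions that a reader might draw are not supported:

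- That no radiologist will ever read the simulated series. The protocol is silent. A research read of anonymised series is possible, and the planned radiologist comparison is compatible with one. Such a read would not be a clinically achieved detection rate, however, and that is what the rule sets out to maintain.
- That all 40 series sit in training. One sentence says so, but another assigns the prospective data to training and testing.
- That sensitivity for genuine cases must fall. This needs both pooled matching and simulated cases that are easier for the model. The second is plausible, because these series contain no gadolinium and the learning task is uptake versus no uptake, but the protocol does not say it.

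It is also fair that this is a pilot and that the AUC does not depend on any cut-off. Net benefit is defined at a chosen risk threshold that the protocol does not tie to the matched cut-off.

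**Conclusion.** The point holds as a defect in how the working point is specified, and it should be fixed. Read literally, the rule can compare sensitivities from different case sets. With pooled matching it then meets its stated aim only if the model detects simulated and genuine cases equally well.

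The main illustration is a loss of 4 to 8 percentage points in sensitivity for genuine cases (0.86 to 0.82 against 0.90). It rests on pooled matching, 50 genuine and 40 simulated training positives, an assumed radiologist sensitivity of 0.90, and detection of 95% to 100% of simulated cases. The loss is larger if the radiologist's sensitivity is lower or if fewer genuine cases are in training. It is zero with equal difficulty and reverses if simulated cases are harder. These figures show what the rule permits; they do not predict the result.

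The results at stake are the secondary sensitivity, specificity and McNemar results, and the false-positive comparison with the clinical reference. A reader might infer that the primary analysis is invalid, but the AUC is untouched by the choice of cut-off.

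**What to change.** In the Data Analysis Plan, state that the cut-off is selected only on genuine clinical exams that have a radiologist clinical assessment, and that model and radiologist sensitivity are computed on the same exams. Add that the simulated pre-contrast series may be used to fit model weights, but do not enter cut-off selection or any paired model-versus-radiologist comparison, and that any model performance on them is reported separately.

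Two statements need to be reconciled at the same time:

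- The sensitivity-matched cut-off in the Data Analysis Plan and the specificity-based threshold in the Test Phase item of Study Procedure. In general one cut-off cannot match the radiologist on both, so the protocol should say which one defines the working point.
- The two sentences in Study Procedure on whether the prospective series serve training only or training and testing.

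The cost is a few sentences and a less precise cut-off, because it would rest on at most 50 positives instead of up to 50 + 40 = 90. No additional patients or imaging are needed.

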This IRB application outlines the part of the study which will involve the collection prospective data for training the machine learning model.

Background (*Include relevant experience, gaps in current knowledge, preliminary data, etc.*):

In 2015, an estimated 17 million magnetic resonance imaging (MRI) examinations were performed in the United States using intravenous (IV) contrast agents [1], reflecting the essential role of IV contrast in the detection, characterization, and staging of disease. On occasion, the IV line is inadequate and causes the contrast medium to infiltrate into the muscle tissue in the arm, which can cause discomfort to the patient, delays with the patient scan as well as the need for a repeat exam to be performed or patient call-back, if not detected in a timely manner. The risk of undetected contrast medium extravasation is increased when automated mechanical injectors or higher injection rates are used for the contrast material injection [2-3]. Thus, if the occurrence of IV infiltration could be detected during the patient MR examination before the patient is removed from the scanner this would significantly improve both the patient experience and the clinical workflow. To that end, this study aims to develop a machine learning algorithm to detect intravenous infiltration, into the muscle of MR contrast agent used for routine brain MR examinations, through the analysis of the nasal mucosa.

Study Design and Methods

Methods: *Describe in lay terms, completely detailing the research activities that will be conducted by Mayo Clinic staff under this protocol.*

We will recruit 40 patients presenting for a clinical Magnetic Resonance Imaging (MRI) brain without and with IV contrast agent. Informed written consent will be obtained prior to the participation in the study and recorded in clinical documents. Each patient will be contacted by the principal investigator or one of his/her designees. The potential risks to participants will be minimal. The specific absorption rate (SAR) used in this study is well under the current FDA safety limits for MRI. No additional drugs or invasive procedures will be used in the study.

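### Net benefit, a primary measure, is defined on raw test-cohort counts, so it is capped at that cohort's case share and overstates clinical net benefit if infiltrated cases are over-represented

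*Protocol*

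**What the plan says.** The Endpoints section of the protocol gives the primary endpoint as "Primary: Area-under-curve performance for each machine learning model and the performance measure" net benefit. Both terms of the formula are counts over the "Total number of patients", and the weight w "corresponds to the odds (i.e. the harm-to-benefit ratio) of the chosen risk threshold". The Figure 1 legend says that net benefit is evaluated in the unseen test cohort, after a recalibration step on a separate dataset. Neither place mentions a clinical infiltration rate or any re-weighting to one.

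On how common the event is, the Background says only: "On occasion, the IV line is inadequate and causes the contrast medium to infiltrate into the muscle tissue in the arm". On the material, Study Procedure says that "currently there is a low number of previous studies (n= 50) with associated MR images demonstrating IV infiltration", and that scans simulating infiltration will be obtained from 40 patients.

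The role of those simulated scans is not clear. One sentence has them "stored for subsequent analysis using the machine learning model as part of the training phase". Another has them "used to augment the retrospective data already collected for the training and testing of the developed AI algorithm". Research Question and Aims describes this application as "the part of the study which will involve the collection prospective data for training the machine learning model".

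**The concern.** Net benefit is meant to put true and false alarms on one scale for the patients in whom a model will be used, so prevalence is part of its meaning. The stated formula has no separate prevalence term and takes whatever case share the test cohort has. If infiltrated studies are gathered because they are scarce, and then tested against a limited number of non-infiltrated scans, the result describes that mixture and not routine brain MR.

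At stake is the size of a reported primary measure. A reader may be unable to convert it. The Data Analysis Plan sets cut-offs to match radiologist sensitivity, and the reported sensitivity and specificity may refer to those cut-offs. They need not be the risk threshold behind w.

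**Working it through.** The protocol states no net benefit value, so there is no figure to reproduce.

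**Inputs.** From the protocol: the formula, w as the odds of a risk threshold, 50 infiltrated studies, and 40 patients giving simulated scans. Not given, and therefore assumed below: case share, clinical rate, Se, Sp and threshold.

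**1. Rewrite the formula.** With N patients and case share π_s, TP/N = Se·π_s and FP/N = (1 − Sp)(1 − π_s). Hence NB = Se·π_s − (1 − Sp)(1 − π_s)·w. Check with TP 36, FN 4, FP 6, TN 54 and w = 0.1/0.9:
- counts: 0.36 − 0.06 × 0.1111 = 0.3533
- rewritten form: 0.90 × 0.40 − 0.10 × 0.60 × 0.1111 = 0.3533

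**2. Cap.** A perfect model (Se = Sp = 1) scores π_s. No model can score more.

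**3. Direction.** At a given cut-off, the slope of NB in the case share is Se + (1 − Sp)·w, which is positive. So a case share above the clinical rate always raises the value. Recalibration moves the cut-off but does not undo this. Every cut-off scores less at the lower rate, so the best one does too.

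**4. Size.** Assumed Se 0.90, Sp 0.95, threshold 10% (w = 0.1111). Flag-all = π − (1 − π)·w; flag-none = 0.

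| Case share | Perfect model | Assumed model | Flag-all |
|---|---|---|---|
| 50% | 0.50 | 0.4472 | 0.4444 |
| 10% | 0.10 | 0.0850 | 0.0000 |
| 1% | 0.01 | 0.0035 | −0.1000 |

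Example at 1%: 0.90 × 0.01 − 0.05 × 0.99 × 0.1111 = 0.0090 − 0.0055 = 0.0035.

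**5. Are these cells possible with calibrated risks?** Flagged patients must have a risk of at least 10%, and unflagged patients at most 10%.
- At 50% cases, unflagged risk = 0.05/(0.05 + 0.475) = 9.5%.
- At 1% cases, flagged risk = 0.009/(0.009 + 0.0495) = 15.4%.

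Both pass. If recalibration to 1% moved the cut-off and did no worse than the old one, net benefit would lie between 0.0035 and the cap of 0.0100, against a raw 0.447 at 50% cases.

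**6. The threshold shifts too.** Clinical odds = sample odds × [π/(1 − π)]/[π_s/(1 − π_s)]. A predicted 10% risk calibrated at 50% cases has odds 0.1111. At a 1% rate this becomes 0.1111 × 0.0101 = 0.0011, a risk of about 0.11%.

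**7. What would make the raw value transportable?** For a 1% case share, c test cases need c/0.01 − c non-infiltrated scans: 4,950 for all 50 known cases, 990 for 10. The protocol describes no such number, but does not exclude it.

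**8. Ranking.** At equal sensitivity, two models differ by (Sp₁ − Sp₂)(1 − π)·w. The sign does not depend on π.

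**The case against.** The formula is the standard definition of net benefit, and its algebra is sound. It misdescribes clinical use only if the test cohort is enriched. The protocol states neither that cohort's make-up nor the clinical rate. This application is limited to collecting prospective training data, and the simulated scans may never reach testing. The retrospective test set could be a consecutive series. All of this stands, so enrichment remains an inference.

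A SAP could supply the threshold, the comparators and a reference rate, and their absence here is no fault. But the protocol itself fixes the endpoint as raw counts, and a SAP that followed it would report the raw value. The investigators could recompute from retained predictions. That makes the repair cheap but does not make the stated definition fit for clinical use.

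Three stronger readings are tempting, and the documents do not support them.
- *A reader might infer that the model would have negative clinical net benefit.* With the assumed Se and Sp and a 20% threshold (w = 0.25), the 1% cell is 0.0090 − 0.05 × 0.99 × 0.25 = −0.0034. But flagged risk is then 15.4%, below the 20% threshold, which cannot occur with calibrated risks. Negative values, and any break-even rate built on them, describe use without recalibration to the clinical rate.
- *A reader might infer that the raw value can hide a model worse than flagging everyone.* At 50% cases and a 5% threshold, flag-all scores 0.474 and the assumed model 0.449. But unflagged risk is then 9.5%, above 5%, so the same limit applies.
- *A reader might infer that the wrong model would be chosen.* Selection is by AUC on the validation set, before net benefit is computed in the test cohort, and cut-offs are matched on sensitivity. A change of order is possible only where models trade sensitivity against specificity at the threshold behind w.

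**Conclusion.** The point holds in a limited form. As defined, net benefit cannot exceed the test-cohort case share. If that share exceeds the clinical infiltration rate, the raw value overstates clinical net benefit. Enrichment is the natural reading of the protocol but is not proven.

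The overstatement can be large: the ceiling falls from 0.50 to 0.01 between 50% cases and an assumed 1% rate. For the assumed model at a 10% threshold, a raw 0.447 also exceeds flag-all by only 0.4472 − 0.4444 = 0.0028, so its size alone says little about usefulness. These figures rest on assumed rates, Se, Sp and threshold, since the protocol gives none.

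The consequence is confined to the reported value of one of the primary measures. AUC is not affected, this is a declared pilot, and nothing is decided on net benefit. The definition should be corrected, but the study design is not in question.

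**What to change.** Amend the net benefit definition in the Endpoints section as follows.
- Report NB = Se·π − (1 − Sp)(1 − π)·w at a pre-stated clinical infiltration rate π, with a range. Take π from site records if a denominator exists; otherwise state an assumed range.
- Recalibrate predicted risks to π, and take Se and Sp at the risk threshold that defines w.
- Show flag-all and flag-none at the same π.
- Keep the raw sample value as a supplementary figure, with the test-cohort case share stated and a note that it does not carry over to clinical use.
- If values with Se and Sp held fixed across case shares or thresholds are shown, label them as use without recalibration.

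The cost is the wording of one endpoint and a few lines of code, with no change to data collection. The downside is a smaller headline figure that depends on an external or assumed rate.
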